## Background

Summarize in 2-3 paragraphs past experimental and/or clinical findings leading to the design of this protocol. Include any relevant past or current research by the PI. For drug and device studies, summarize the previous results (i.e., Phase I/II or III studies).

Smoking remains the leading cause of preventable death in the U.S. with approximately 18% of the population continuing to smoke. However, smoking is concentrated in disadvantaged populations where the prevalence of smoking may be as high as 70-80 %. Participants will receive a sampling experience (use of nicotine lozenges or NicoBloc during sessions) with counseling focused around their experience of using these interventions, including side effects and smoking cessation expectancies.

NicoBloc is a pink occlusion fluid supplied in 15 ml bottles. Three drops applied to a cigarette filter will trap up to 99% of tar and nicotine in the filter (depending upon cigarette brand). The ingredients of NicoBloc are: Corn Syrup (86.83%), Water (12.76%), Citric Acid (E330) – acidity regulator (0.30%), Sodium Benzoate (E211) – food preservative (0.05%), Potassium Sorbate (E202) – food preservative (0.05%), Allura Red 40 (E129) – red food colouring (0.01%). These ingredients are classified as FDA approved food grade ingredients.

#### **Procedure**

A urine drug screen and pregnancy test for females will be obtained during the screen visit. If positive, participants will be screen failures and will not be enrolled in the study. Specimens will not be

distributed or stored. They will be labeled with a unique study identifier. There will be no clinical data associated with the specimens. They are used only to establish eligibility for the study.

After eligibility determination and consent to participate, the baseline assessments will be administered. This assessment is expected to take about 60 minutes and will provide basic smoking history, smoking behavior, and proposed mediators and moderators such as treatment interest, expectancies for NRT and NicoBloc, previous use of NRT, craving, withdrawal, and side effects associated with NRT use (see Table 1 description) and will be repeated during the study period (see Table 2 for assessment schedule). At each visit the participant will have a carbon monoxide test (CO) which will determine how much CO is in the lungs. At the baseline visit, participants will be asked to prolong smoking as long as they can on the days of the study sessions. Female participants will be screened monthly for pregnancy.

Participants will be randomized to either NicoBloc or Nicotine Lozenge and will undergo the following interventions. Interventionists will be undergraduate level research assistants (RAs) with degrees in psychology or a related field. They will be trained to follow the manual and deliver both behavioral interventions by the PI, although they will not have extensive tobacco training. All sessions will be audiotaped and 20% will be coded for treatment fidelity to ensure no contamination between behavioral interventions.

NicoBloc: NicoBloc participants will be provided with NicoBloc to use in each 30-minute session and will test smoking their conventional cigarette with NicoBloc. In session, they will discuss their experience of smoking their cigarette with NicoBloc at each of the sessions. For Session 1, participants will use one drop of NicoBloc (which will block 33% of tar and nicotine) on their conventional cigarette and then will smoke this cigarette in session. Following smoking, they will discuss the effects of the NicoBloc on their withdrawal, cravings, and overall enjoyment of their cigarette. To bolster their in vivo NicoBloc experience, participants will be provided with NicoBloc to use between sessions to acclimate to the NicoBloc and to make practice quit attempts (PQAs). Sessions 2 and 3 are similar to Session 1 except they will use more NicoBloc product during the session and will be instructed to use the product between sessions. For example, in Session 2, they will use 2 drops on their cigarettes (which blocks about 66% of tar and nicotine) and then smoke. Similarly, in Session 3 they will use 3 drops of NicoBloc which is equivalent to blocking 99% of the tar and nicotine exposure from a cigarette and then smoke. At Session 4 they will discuss their experiences using NicoBloc and will set a quit date prior to their 8 week visit. Participants will return at 8 and 12 weeks (EOT) with a final one month follow-up at Week 16.

Nicotine Lozenge: Participants who receive nicotine lozenge (mini lozenge) will be given either a 2 or 4 mg lozenge to use in session, depending on how soon they smoke after waking. If a participant smokes within 30 minutes of waking, they start with the 4 mg lozenge; more than 30 minutes, they start with the 2 mg lozenge. Similar to NicoBloc, they will use the lozenge in session and will discuss the effects of using the lozenge in session. They will do this for all four Sessions and will be given lozenges between sessions to make PQAs. They will be asked to set a quit date during Session 4 similar to the NicoBloc participants.

After the four week intervention, participants will be given an additional 8 weeks of medication (NicoBloc or Lozenge) in four week allotments to use for a sustained quit attempt. Thus, both groups will receive the medication for 12 weeks total to make a quit attempt. All participants will continue to receive medication and monitoring for side effects, regardless of their medication adherence. Study visits occur at baseline (Week 0), intervention Weeks 1-4, Week 8, Week 12 (EOT), and then a 1 month follow-up after medication use has ended.

Phone numbers will be collected to send study appointment reminders, missed appointment notifications only or if the participant needs to be reached concerning the study.

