#### **Purpose**

This pilot study will examine the feasibility, acceptability, and preliminary impact of using NicoBloc compared to nicotine lozenges. Forty (n=40) participants will be randomized to one of two interventions 1) NicoBloc or 2) nicotine lozenge. All participants will complete approximately 60 minutes of baseline assessment to determine smoking history and characteristics prior to randomization, including previous experience with NRT.

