A Pilot Trial Comparing NicoBloc to Nicotine Lozenges: Initial Acceptability and Feasibility Trial 2/2/2022 NTC:300001370

Data Analytic Approach

Participant screening, baseline eligibility, baseline attendance, study eligibility, and retention rates throughout the study were calculated overall and per time point. Retention rates between groups at each time point and other dichotomized variables such as adherence were assessed using Chi-Square analyses. Participant demographics and baseline smoking characteristics were assessed, and group differences examined using measures of effect size (Cramer's *V* and Cohen's *d*). Group differences over time were analyzed using generalized estimating equations (GEEs) with all available data (i.e., Intent-To-Treat analyses). GEE results were followed-up with pairwise comparisons when applicable. Measures administered pre- and post-session (QSU and MNWS) were calculated as a change score and included as such in GEE analyses. Pre-session scores were subtracted from post session scores such that negative scores reflect decreases in withdrawal symptoms or smoking urges throughout the session. For measures administered at two or less time points, *t*-tests were used to examine group differences.

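### No baseline covariate is named for any group comparison, although time to first cigarette sets lozenge strength and other smoking measures are taken at baseline; adjustment would be a cheap gain in precision

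*Protocol*

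**What the plan says.** **Protocol.** Under Purpose: "Forty (n=40) participants will be randomized to one of two interventions". No allocation ratio is given. The same section places a "baseline assessment to determine smoking history and characteristics prior to randomization". Under Procedure, the baseline assessment "will provide basic smoking history, smoking behavior, and proposed mediators and moderators", with craving and withdrawal among the examples, and CO is measured at every visit. Allocation is described only as "Participants will be randomized to either NicoBloc or Nicotine Lozenge and will undergo the following interventions"; no stratification, blocking or minimisation is mentioned. In the lozenge arm the starting strength follows one rule: "If a participant smokes within 30 minutes of waking, they start with the 4 mg lozenge", and later first smokers start on the lower strength. The NicoBloc arm has no counterpart to this rule.

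**SAP (Data Analytic Approach).** Baseline balance is handled descriptively: "Participant demographics and baseline smoking characteristics were assessed, and group differences examined using measures of effect size", namely Cramer's V and Cohen's d. Nothing is said about what follows if a difference is seen. For repeated measures, "Group differences over time were analyzed using generalized estimating equations (GEEs) with all available data"; no model terms are listed. For binary outcomes, retention and "other dichotomized variables such as adherence were assessed using Chi-Square analyses". Measures taken at no more than two time points are compared by t-test. QSU and MNWS enter the GEEs as post-session minus pre-session change scores.

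**The concern.** The protocol treats time to first cigarette as important enough to change what a participant receives. It is plausibly related to craving, withdrawal, CO and product use, though the documents do not show this. In a trial of 40 people without stated stratification, a sizeable chance difference between arms on any binary factor is quite likely. The SAP would show such a difference through an effect size but plans no step that takes it into account. Choosing covariates after seeing the imbalance would be data-driven, so the choice has to be made in advance.

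Two things are at stake. One is precision, which is scarce in a pilot meant to give a preliminary estimate of impact. The other is bias in the particular randomisation obtained if the arms happen to differ on a prognostic factor. Stratifying 40 people is a genuine trade-off. Adjusting for one binary baseline variable is much less of one.

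**Working it through.** The documents give no power, alpha, effect size or derivation for n = 40, so there is no planned figure to reproduce.

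**Inputs from the documents:** 40 randomised, two arms (Protocol, Purpose); 70% retention target (Protocol, Analysis strategy).

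**Assumed inputs:** 1:1 allocation, hence 20 per arm; share p smoking within 30 minutes of 0.4 to 0.7, with 0.8 as a further case; effect g of this factor on an outcome of 0.5 to 1.0 SD, with 0.2 as a low case; two-sided alpha 0.05.

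**1. Chance of imbalance.** The difference of two independent Binomial(20, p) proportions, enumerated exactly (p = 0.4 equals p = 0.6 by symmetry):

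| p | gap of at least 20 points (4 people) | gap of at least 30 points (6 people) |
|---|---|---|
| 0.5 | 26.8% | 8.1% |
| 0.4 or 0.6 | 25.8% | 7.5% |
| 0.7 | 22.6% | 5.6% |
| 0.8 | 16.4% | 2.9% |

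At 70% retention, 0.7 × 20 = 14 remain per arm. If dropout is unrelated to the factor, a gap of at least 20 points (in practice 3 people, 3/14 = 21 points) has probability 30-35% for p from 0.4 to 0.7, and 23% at p = 0.8.

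**2. Shift in the group difference** = imbalance × g.
- 20 points: 0.20 × 0.5 = 0.10 SD; 0.20 × 1.0 = 0.20 SD; low case 0.20 × 0.2 = 0.04 SD.
- 30 points: 0.30 × 0.5 = 0.15 SD; 0.30 × 1.0 = 0.30 SD.
- Standard error of the difference = √(2/20) = 0.316 SD. The 20-point shift is therefore 0.10/0.316 = 0.32 to 0.20/0.316 = 0.63 of one standard error.

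**3. Type I error of the unadjusted t-test.** Simulation of 100,000 trials per effect size, 20 per arm, p = 0.7, residual SD 1:

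| g | all randomisations | given a gap of at least 20 points |
|---|---|---|
| 0.2 | 5.0% | 5.3% |
| 0.5 | 5.0% | 6.2% |
| 0.8 | 5.1% | 7.8% |

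**4. Gain from adjustment.** Power = Φ(d / [√(1 − R²) × √(2/20)] − 1.96), total SD 1, ignoring the lost degree of freedom:

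| d | unadjusted | R² = 5% | R² = 10% | R² = 20% |
|---|---|---|---|---|
| 0.5 | 35.2% | 36.8% | 38.5% | 42.4% |
| 0.8 | 71.6% | 73.7% | 76.0% | 80.7% |

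For orientation, at p = 0.7 the factor explains R² = 0.21g²/(1 + 0.21g²): 0.0525/1.0525 = 5% at g = 0.5 and 0.21/1.21 = 17% at g = 1.0.

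**5. Week 0 value of the outcome.** If it correlates 0.5 with the later value (assumed), adjusting for it removes 0.5² = 25% of the variance. That is more than time to first cigarette removes under any of the effects assumed here.

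**The case against.** The case against is substantial, and several parts of it stand.

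- **What is stated and what is inferred.** A reader might infer that time to first cigarette is excluded from every comparison. The documents do not support that. The t-tests and chi-square tests are unadjusted by nature, but the SAP lists no GEE terms at all, so for those models one can say only that no covariate is named. Recording of the factor in both arms is likewise an inference: smoking history is collected before randomisation, but this item is not named, and the protocol's assessment tables are not in the available text.
- **Validity.** A reader might also infer that any imbalance passes in full into the results, or that the tests are invalid. Neither follows. Only imbalance times prognostic effect carries through, which is less than one standard error in every case above, and randomisation keeps overall type I error near 5%.
- **Prognostic strength is assumed.** A dosing rule in one arm does not show that the factor predicts these outcomes. At 0.2 SD the effect is negligible.
- **Change scores.** For QSU and MNWS, a stable effect of dependence on level is at least partly differenced out, so an effect on level cannot be carried over directly.
- **Link to the primary outcomes.** These are feasibility, acceptability and adherence, and recruitment is not an arm comparison. Adherence is a comparison between arms, however, and its chi-square test is unadjusted.
- **Timing.** The SAP is written in the past tense. If the analyses are already done, adjustment is no longer prespecified.

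The descriptive balance check is sensible for a pilot, but it leads to no action. These points limit the size of the concern without removing the case for a cheap improvement.

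**Conclusion.** The point holds as a minor one. The SAP names no baseline covariate, although relevant baseline measures exist and one related characteristic determines lozenge strength. At this sample size an imbalance of 20 points or more on that characteristic has roughly a one-in-four chance, falling to about one in six if 80% smoke within 30 minutes. The resulting shift is modest against the standard error, and the gain in power is a few percentage points for most of the assumed values. The cost of leaving the plan unchanged is lower precision and conditional bias when an imbalance occurs; it is not an inflated overall error rate.

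The conclusion rests on assumed 1:1 allocation, prevalence, prognostic effect, R² and alpha, none of which the documents give. The recommendation depends little on them, because adjustment costs so little.

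**What to change.** 1. State that time to first cigarette (within 30 minutes of waking, yes or no) is recorded in both arms before randomisation, and name it in advance as a covariate in the GEEs. Use this characteristic, not lozenge strength, which is part of the assigned treatment and exists in one arm only.
2. Where an outcome has a Week 0 value, add that value as a covariate and model only post-baseline visits as responses, so that Week 0 is not used twice.
3. For QSU and MNWS session change scores, adjust for the pre-session or Week 0 level and say which. Week 0 is the safer choice across sessions, because pre-session scores from Session 2 onward follow product use and may themselves be affected by treatment.
4. Replace the t-tests with the same adjusted comparison (ANCOVA).
5. Report a covariate-adjusted estimate for dichotomised adherence alongside the chi-square test.

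**Cost:** a short addition to the SAP, one or two degrees of freedom and a little more analysis work. No visit, dose or sample size changes. If the data have already been analysed, the adjusted results should be labelled as a sensitivity analysis.

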A Pilot Trial Comparing NicoBloc to Nicotine Lozenges: Initial Acceptability and Feasibility Trial 2/2/2022 NTC:300001370

Data Analytic Approach

Participant screening, baseline eligibility, baseline attendance, study eligibility, and retention rates throughout the study were calculated overall and per time point. Retention rates between groups at each time point and other dichotomized variables such as adherence were assessed using Chi-Square analyses. Participant demographics and baseline smoking characteristics were assessed, and group differences examined using measures of effect size (Cramer's *V* and Cohen's *d*). Group differences over time were analyzed using generalized estimating equations (GEEs) with all available data (i.e., Intent-To-Treat analyses). GEE results were followed-up with pairwise comparisons when applicable. Measures administered pre- and post-session (QSU and MNWS) were calculated as a change score and included as such in GEE analyses. Pre-session scores were subtracted from post session scores such that negative scores reflect decreases in withdrawal symptoms or smoking urges throughout the session. For measures administered at two or less time points, *t*-tests were used to examine group differences.

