### **Analysis strategy**

Feasibility and acceptability will be measured through high study retention (70%) and recruitment (recruitment of all participants within 24 months) in our groups. Additional items of acceptability include high scores on treatment satisfaction and credibility/expectancies that are equal or higher to the NicoBloc group. Medication adherence is a third primary outcome with expected differences between our groups. Adherence is notoriously difficult to determine. Self-reported adherence is not always reliable, particularly during treatment studies where there is a demand characteristic to report the desired targeted behavior (e.g., adherence to medication). The behavioral methods described under the assessment section represent the best available self-report tools for determining NRT adherence (e.g., Timeline Follow Back (TLFB) report, returning used products and packaging). Adherence will be defined by self-report using the TLFB and verified through returned patches and packaging. Good adherence is defined by taking greater than 80% of doses of medication at each time point.

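### Adherence is a primary outcome with an expected arm difference, but its only stated test is a Chi-square on a dichotomized status; a percent-of-doses comparison and confidence intervals are worth adding

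*SAP*

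**What the plan says.** The protocol's Analysis strategy states: "Medication adherence is a third primary outcome with expected differences between our groups". It measures adherence by Timeline Follow Back self-report, verified from returned product and packaging, and sets a threshold: "Good adherence is defined by taking greater than 80% of doses of medication at each time point".

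The SAP's Data Analytic Approach mentions adherence in one sentence: "Retention rates between groups at each time point and other dichotomized variables such as adherence were assessed using Chi-Square analyses". It does not repeat the 80% cut; linking the dichotomized variable to the protocol's threshold is an inference, though the only one available. The SAP mentions effect sizes ("group differences examined using measures of effect size") only in the sentence on demographics and baseline smoking characteristics. T-tests are reserved as follows: "For measures administered at two or less time points".

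The Procedure section places on-product visits at Weeks 1-4, 8 and 12. Weeks 1-4 are for in-session sampling, acclimation and practice quit attempts. After that, participants receive "an additional 8 weeks of medication (NicoBloc or Lozenge) in four week allotments to use for a sustained quit attempt", so Weeks 8 and 12 close those two supply intervals.

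**The concern.** A percentage is collected, cut at 80%, and tested as yes or no. A participant at 79% then counts the same as one at 5%. With about 20 people per arm, that loss can matter for an outcome on which a difference is expected.

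A p-value is also a poor summary for a pilot. If 10/20 and 15/20 were adherent, the Chi-square would give p=0.10, and a report of no significant difference would hide a 25-point estimate compatible with anything from slightly negative to nearly 50 points.

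Both the status and the percentage need a count of expected doses. The supplied text gives none for either product. NicoBloc is used per cigarette ("Three drops applied to a cigarette filter"), so it is unclear what is expected in an interval in which a participant has stopped smoking.

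**Working it through.** **Inputs.** From the documents: 40 randomised, two arms, 70% retention target, the >80% threshold, on-product visits at Weeks 1-4, 8 and 12. Assumed, because the documents are silent: 1:1 allocation (20 per arm, or 14 at 70% retention), two-sided 0.05, 50% v 75% above the cut, within-person correlation 0.3 to 0.9, complete data. There is no stated power or effect size to reproduce.

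**Step 1. Same visit, status v percentage.** If the percentage is roughly normal, 50% v 75% above the cut is a difference of d = z(0.75) - z(0.50) = 0.674 SD. The t-test has noncentrality d × √(n/2) = 0.674 × √10 = 2.13 on 38 df. The Chi-square power is summed exactly over the two binomials.

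| Per arm | Rates above cut | Chi-square | t-test on percentage |
|---|---|---|---|
| 20 | 50 v 70% | 0.245 | 0.366 |
| 20 | 50 v 75% | 0.375 | 0.547 |
| 20 | 50 v 80% | 0.531 | 0.737 |
| 14 | 50 v 75% | 0.268 | 0.405 |

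For capped, U-shaped, J-shaped or two-lumped percentages with 20 per arm and 50 v 75%, the t-test power is 0.41 to 0.54.

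**Step 2. Two visits, like with like.** The mean of Weeks 8 and 12 has effective d = (average d over the two visits) / √((1+ρ)/2). The fair comparator is each participant's >80% status averaged over the same two visits. Simulated power, near-normal data, 20 per arm (mean percentage v pooled status):

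| ρ | Equal at both visits | Week 8 at 80% of Week 12 | Week 8 at half |
|---|---|---|---|
| 0.3 | 0.733 v 0.566 | 0.641 v 0.487 | 0.491 v 0.356 |
| 0.5 | 0.669 v 0.522 | 0.579 v 0.447 | 0.436 v 0.330 |
| 0.7 | 0.615 v 0.481 | 0.523 v 0.405 | 0.395 v 0.305 |
| 0.9 | 0.569 v 0.428 | 0.483 v 0.364 | 0.358 v 0.272 |

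The gain runs from 0.358 - 0.272 = 0.086 to 0.733 - 0.566 = 0.167, that is, about 9 to 17 points. For heavily capped percentages it is about 5 to 7 points; for two-lumped percentages it is about zero.

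**Step 3. Where the two-visit mean loses.** With a half-size difference at Week 8 and ρ = 0.9, the average d is 0.75 × 0.674 = 0.506 and the SD of the mean is √0.95 = 0.975, so effective d = 0.519 and power is 0.36. Across data shapes the figure is 27 to 37%, against about 38% for a Week 12 Chi-square. If the difference exists only at Week 12, the mean has 19 to 25%.

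**Step 4. The estimate.** For 10/20 v 15/20 the pooled rate is 0.625, so Chi-square = 0.25² / (0.625 × 0.375 × 2/20) = 2.67 and p = 0.102. The difference is 25 points, with Newcombe 95% CI -5 to 49.

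**Step 5. Separate visit tests.** If each visit were tested at 0.05 and any one could count, the chance of at least one false positive would be about 7 to 10% for two visits and 14 to 27% for six. These ranges cover adherence rates of 30 to 70% and correlations of 0.3 to 0.9; the low ends occur near 50% adherence, where the test's actual size is about 4.3%.

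**The case against.** The protocol itself defines good adherence by the 80% threshold, and a Chi-square matches that definition. Self-reported adherence is, by the protocol's own account, not always reliable, which makes a coarse cut defensible. This is a 40-person pilot with no power claim, so low power contradicts nothing planned. All of that stands, and it is why the status should be kept.

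The percentage also brings problems of its own. It needs a dose denominator for each arm, and a zero or ambiguous denominator can distort a mean more than a yes/no status. A Weeks 8 and 12 summary omits four of the six on-product visits. The power gain depends on a distribution the documents do not describe.

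A reader might infer more than the text supports:
- That the >80% status should be replaced. Steps 2 and 3 do not support that for every plausible data shape or timing of effect.
- That the SAP excludes a longitudinal analysis of adherence. Its GEE sentence on group differences over time does not name adherence but does not rule it out; Chi-square is only the sole test stated.
- That the sponsor plans to pick among visits. The text says nothing of the kind. The threshold's timing can mean one result per visit or above 80% at every visit.
- That a primary visit, dose definition or schedule was never written. The protocol points to an assessment section and tables that are not in the supplied text and may contain them.

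What remains is that a primary comparative outcome has one stated test, which discards the percentage, and the supplied text plans no difference with an interval.

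**Conclusion.** The point holds as a suggested improvement, not as a flaw that invalidates the planned test. Under the assumed 20 per arm and 50% v 75%, dichotomizing at one visit takes power from 55% to 37% if the percentage is roughly normal. Over the same two visits the cut costs about 9 to 17 points for near-normal data, less when values pile up at 100%, and about nothing when participants are either near-full or near-zero users. If the difference is mostly at Week 12, the two-visit mean can do no better, or worse, than a Week 12 Chi-square. The case for an estimate with an interval does not depend on these assumptions.

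**What to change.** 1. Keep the >80% rate as the protocol's definition of good adherence, and report it as a between-arm difference with 95% CI. Say whether the threshold applies visit by visit or must be met at every visit.
2. Beside it, add one between-arm comparison of percent of expected doses taken: each participant's mean of the available Week 8 and Week 12 values, by t-test, with the difference and 95% CI.
3. Name one of the two in advance as the main adherence result. That also removes the multiple-visit question for it.
4. State for each arm what counts as a dose and the expected number per interval, including intervals in which a NicoBloc participant smokes no cigarettes. The >80% status needs the same denominator. If the assessment section already gives this, cite it.
5. The SAP is written in the past tense. If outcome data have already been analysed, label the percent-of-doses analysis post hoc and show it beside the Chi-square.

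The cost is SAP wording and a little analysis, with no new data provided the dose counts can be defined from what is collected. The added comparison leaves out Weeks 1-4, can lose power if the difference appears late, and, because it uses available visits, assumes that missed visits are unrelated to unseen adherence.

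### The SAP states no small-sample correction for GEE with about 20 participants per arm; run in the usual form, nominal 5% tests would have a true size of about 6–10%

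*SAP*

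**What the plan says.** The SAP (Data Analytic Approach) gives one method for comparing arms across time: "Group differences over time were analyzed using generalized estimating equations (GEEs) with all available data". The only GEE outcomes it names are session-level: "Measures administered pre- and post-session (QSU and MNWS) were calculated as a change score and included as such in GEE analyses". It adds that "GEE results were followed-up with pairwise comparisons when applicable". It does not state the working correlation, robust or model-based standard errors, the test statistic and its reference distribution, whether session is linear or categorical, the significance level, or any small-sample adjustment.

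The protocol fixes the size of the trial: "Forty (n=40) participants will be randomized to one of two interventions" (Purpose). The allocation ratio is not given.

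The number of sessions that contribute is not settled by the text. For lozenge participants, in-session product use is described throughout: "They will do this for all four Sessions and will be given lozenges between sessions to make PQAs". For NicoBloc, product use is described for Sessions 1 to 3, and then: "At Session 4 they will discuss their experiences using NicoBloc and will set a quit date prior to their 8 week visit" (both Procedure). The protocol refers to a Table 2 for the assessment schedule, but that table is not in the text available to us.

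**The concern.** GEE inference rests on the number of independent participants being large. With about 20 per arm, two things go wrong with the usual output. The robust sandwich covariance is biased downward, because residuals are smaller than the errors they stand in for. The Wald chi-square also treats that covariance as known, although it is estimated from few participants. Both make p-values too small and intervals too narrow, and the effect grows with the degrees of freedom of the test. A categorical group-by-session interaction is therefore hit harder than a linear trend. Pairwise follow-ups use the same standard errors.

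At stake is how the preliminary-impact comparisons are read. A difference in urges or withdrawal over sessions could be reported as significant at 5% when the test's real false-positive rate is higher.

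**Working it through.** The documents give no type I error, power or sample-size figure, so there is nothing of the plan's own to reproduce.

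**Inputs.** From the documents: N = 40 in two arms; GEE on one change score per session; four sessions, or three if NicoBloc Session 4 yields no pre/post pair. Assumed, because not stated: 1:1 allocation (m = 20 per arm), a nominal 5% level, and the uncorrected robust Wald chi-square.

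**Closed form for the uncorrected test.** With complete, balanced Gaussian data, the robust Wald statistic for the interaction equals Hotelling's T² × m/(m−1), because the sandwich divides by m where the unbiased covariance divides by m−1. Under the null, T² × (2m−1−q)/(q(2m−2)) follows F(q, 2m−1−q), where q is the degrees of freedom of the test. So, with c the 95% chi-square point:

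size = P( F(q, 39−q) > c × (19/20) × (39−q)/(38q) )

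- q = 1 (linear time, or one pairwise comparison): 3.841 × 0.95 × 38/38 = 3.649; size 6.4%.
- q = 2 (three categorical sessions): 5.991 × 0.95 × 37/76 = 2.771; size 7.6%.
- q = 3 (four categorical sessions): 7.815 × 0.95 × 36/114 = 2.344; size 8.9%.

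These values do not depend on the within-person correlation.

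**Simulation.** Two separately programmed simulations (4,000 null replicates per scenario, Monte Carlo error about 0.3–0.5 points) covered four sessions, 70–100% retention at the last session, and exchangeable and AR(1) correlation. With Gaussian scores the uncorrected robust test rejected 5.5–7.1% of the time with linear time and 8.6–10.5% with categorical sessions. The last-session pairwise comparison rejected 6.3–7.5%. With skewed or floored scores the three ranges were 5.8–6.9%, 7.8–9.9% and 5.8–7.3%. Three categorical sessions, run under AR(1) 0.5 with 70% retention, gave 7.5%.

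**Closed form for the remedy.** Mancl-DeRouen inflates the covariance, so that the statistic becomes T² × (m−1)/m. Referred to F(q, N−2), the critical value on the Wald scale is q × F₀.₉₅(q, 38), and

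size = P( F(q, 39−q) > critical value × (20/19) × (39−q)/(38q) )

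- q = 1: critical value 4.10; size 4.5%.
- q = 3: critical value 8.56 instead of 7.81; 8.555 × 20/19 × 36/114 = 2.844; size 5.1%.

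Two variants are worse for q = 3. Mancl-DeRouen with a chi-square reference still gives 6.7%. Mancl-DeRouen with the Hotelling critical value 3 × (38/36) × F₀.₉₅(3, 36) = 9.08 corrects twice and gives 4.2%.

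One simulation used the closely related reference F(q, N−p), p being the number of regression parameters. It gave 3.8–5.3% (linear) and 4.5–5.7% (categorical), and 3.9% for both with skewed scores.

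**Cost.** Interval ratio at N = 40: (2.024/1.960) × (20/19) = 1.087. For power, the noncentrality was set so that the uncorrected test rejects 80% of the time; the noncentral F then gives about 75% (q = 1) and 71–72% (q = 3) for the corrected test.

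**The case against.** The strongest reply is that the documents do not show the uncorrected form was used. A package default, a model-based covariance or an unreported correction could have been in place. That stands, and it makes every inflation figure here conditional. It does not remove the point, because the other common default is not reliably safe. Model-based errors with an exchangeable working correlation gave 5.2–5.9% when that correlation was right. When the truth was AR(1) with correlation 0.7, they gave 13.9% for linear time.

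The second reply is that this is a pilot. The criteria in the protocol's Analysis strategy are retention, recruitment, satisfaction and credibility, and adherence. The SAP assigns retention and adherence to chi-square tests. This also stands: nothing in the documents ties a decision to a GEE p-value.

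Three stronger readings are tempting but not supported:

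- A reader might infer that the false-positive rate is 9–10% in general. That range needs four categorical sessions all contributing, which the NicoBloc Session 4 description leaves open. It is about 7.6% with three and 6–7% with linear time.
- A reader might apply the 70% retention benchmark to get 28 analysed and a 3-df size of 11.0%. But the SAP uses all available data, so a participant with any session score contributes. The 70% has no stated time point, and study visits run to Week 16 while the sessions fall in Weeks 1–4.
- A reader might infer that the differences between arms are exaggerated. The sandwich bias affects standard errors, not the estimates.

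**Conclusion.** The omission is real and its likely consequence is modest. Under the usual uncorrected robust Wald chi-square, a nominal 5% group-by-session test on QSU or MNWS change has a true size of about 6–7% (linear time), about 7.6% (three categorical sessions) or about 9–10% (four). Pairwise follow-ups are at about 6–7%. This rests on about 20 per arm, a 5% level and that choice of estimator and test, none of which the documents state. Binary outcomes, unstructured working correlation and non-random dropout were not examined.

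The harm is overstated precision in the preliminary-impact comparisons. It does not reach the feasibility and acceptability criteria. This is a minor point, worth acting on because the better method is readily available.

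**What to change.** Keep GEE. Add one sentence to the SAP naming the working correlation, the coding of session, the covariance estimator and the reference distribution. We suggest a Mancl-DeRouen covariance with F(q, N−2) for the group-by-session test and t(N−2) for pairwise comparisons, N being the participants who contribute data to that analysis. Do not pair Mancl-DeRouen with the Hotelling critical value. A permutation test of the arm labels is an acceptable alternative.

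The SAP is written in the past tense, so the analyses may already be done. If they were run uncorrected, re-run them and report both versions.

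The cost is that sentence, possibly a re-run, and the loss of precision and power computed above: pairwise intervals about 9% wider and a rejection rate 5 to 9 points lower where the uncorrected test would reject 80% of the time. The corrected test may also be somewhat conservative for strongly skewed scores.
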